4.4 Primary Outcome (Safety population)

The number and percentage of patients experiencing an adverse event (AE) will be summarised by treatment group and overall. Further tabulations in the same format will be reported for subsets of AEs according to the following criteria:

- Serious adverse events (SAEs)
- AEs starting after the commencement of NAC treatment and within 7 days of consent
- SAEs starting after the commencement of NAC treatment and within 7 days of consent
- Intensity (mild/moderate/severe)
- Treatment given in response to AE (yes/no)

- Outcome (recovered/improved/unchanged/deterioration/death)
- Relationship to NAC (unrelated/possibly related/probably related/definitely related)
- Relationship to PP100-01 (unrelated/possibly related/probably related/definitely related)
- Action taken with NAC (none/interrupted/stopped entirely)
- Action taken with PP100-01 (none/interrupted/stopped entirely)¹
- Unexpected with, and related to, NAC
- Unexpected with, and related to, PP100-01
- Suspected unexpected serious adverse reaction (SUSAR), subcategorised into SUSAR to NAC; SUSAR to PP100-01; SUSAR to NAC and PP100-01

The number and percentage of patients experiencing an adverse event will also be reported according to MedDRA system organ class (SOC). Results will be presented separately for AEs not classified as serious, for SAEs and for all AEs. Events will be summarised by (a) treatment group and overall, and (b) by treatment received (NAC or PP100-01+NAC) within each dosing cohort.

Primary analysis

The numbers of participants experiencing AEs and SAEs will be reported by treatment group and overall using the proportion and exact 95% confidence interval. AE and SAE proportions will be compared within each dosing cohort between the PP100-01+NAC and the NAC alone patients using a difference in proportions and its exact 95% confidence interval. AE and SAE rates will be compared between each of the PP100-01 2µmol/kg, 5µmol/kg and 10µmol/kg groups and the combined NAC alone group in the same way.

If the limited sample size or a small number of observed events leads to a lack of interpretability of the formal analysis confidence intervals, the analysis of the primary outcome will be restricted to descriptive summaries only.

Missing data

We do not anticipate missing data impacting on the analysis of the routinely recorded adverse event data that form the primary outcome.

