2.2.2 Adverse Events in NAC Treatment

Although very effective for preventing APAP-induced hepatotoxicity, particularly when used within 8hrs of overdose, intravenous NAC is associated with adverse reactions and administration errors.

Depending on study type, selection criteria, definition of reactions, the rate of adverse reactions varies from <10% to over 50% (Lynch et al 2004; Mullins et al 2004), with adverse reactions commonly associated with the very high blood NAC concentration attained during the 150 mg/kg loading dose.

Nausea and vomiting are extremely common in patients receiving NAC, occurring in 70.4% and 60.4% respectively in a recent cohort of 169 patients treated in Edinburgh (Pakravan et al 2008). The mechanism underlying this common adverse reaction remains unclear, but it occurs in patients that develop hepatotoxicity and in those who do not.

In a randomised controlled study, the incidence of anaphylactoid adverse drug reactions was 18% and 14% in patients receiving the initial loading dose of 150 mg/kg NAC over 15 minutes and 60 minutes respectively (Kerr et al 2005). While this study lacked the statistical power necessary to exclude clinically important benefits from the slower initial infusion rate, the results suggest that the slower initial infusion rate should be considered. In the United States, the FDA advised in 2006 that the initial loading dose of NAC be given over 60 minutes.

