Calmangafodipir (PledOx[®]) had a safety profile in this study as would be predicted by non-clinical data. The most common preferred terms for safety reporting in the study (more than 25 events reported in total) were: neurotoxicity, thrombocytopenia, fatigue, nausea, neutropenia, peripheral sensory neuropathy, diarrhea, leukopenia, decreased appetite, anemia, paresthesia, neuropathy peripheral, vomiting and pyrexia. As expected, the frequencies of neurotoxicity, thrombocytopenia and neutropenia that were reported as AEs mirrored the reporting of these symptoms as chemotherapy-induced toxicities analyzed as efficacy data. Grade 2 neurotoxicity occurred in a smaller proportion of patients in the 5 μ mol/kg PledOx[®] group (4.4%, 2 events) compared to placebo (16.7%, 16 events). No other apparent differences between the treatment groups in terms of adverse events.

To date, approximately 150 patients with mCRC received repetitive dosing with calmangafodipir (PledOx[®]). Approximately 240,000 patients have received single doses of the closely related compound mangafodipir at similar or higher doses. No new significant safety data have emerged during the treatment reporting period. Immediate blood pressure fall, severe diarrhoea and severe vomiting, have previously been identified as important potential risks, to be closely monitored as the clinical program progresses.

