3.2 Studies in Overdose Patients

Patients with overdose are a challenging group to study. Treatment decisions need to be made quickly and, as they present with self-harm behaviour, consenting them to clinical study participation has been seen as potentially difficult.

Work both in Edinburgh and overseas suggests (Eddleston et al 2008 and Pakravan et al 2008), however, that these obstacles can be overcome and it is with this background that we developed this protocol to examine a new treatment approach to the most common poisoning seen in the UK.

The 2-phase 12hr acetylcysteine infusion protocol (100 mg/kg over 2hrs: 200 mg/kg over 10hrs) was studied in a formal factorial design against the traditional 3-phase 20.25hrs infusion protocol. The 12hr regimen was associated with very significant reductions in anaphylactoid reactions and vomiting compared with the 20.25hr infusion protocol.

The 12hr acetylcysteine protocol offers clinicians and patients the possibility for better targeting of therapy, fewer adverse effects, a simpler dosing regimen, and shorter hospital stay (Bateman et al 2014).

With the standard intravenous NAC regime, adverse reactions generally occur during or soon after the loading dose, leading to discontinuation of NAC until the reaction subsides. Despite this, patients who have reactions to intravenous NAC do not appear to have worse clinical outcomes.

This study, with a new treatment regime using PP100-01 co-treatment with the 12hr NAC regime, is designed to examine safety, tolerability and explore new experimental biomarkers in serum/plasma such as CK18 and microRNA (MiR122), GLDH and mitochondrial DNA to find new markers that identify organ injury earlier in the disease process than current markers.

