7.1.9 Adverse events

Adverse events/ adverse reactions will be assessed at baseline, 2hr, 2.5hr 10hr, 20hr and 22hr and as part of follow up (section 7.1.10). A full physical exam will be carried out if AEs/SAEs are identified that require a more thorough exam to be performed and this will be recorded on the CRF.

Episodes and incidence of vomiting and retching will be recorded objectively by nursing staff on the AE log and reported as an SAE if classified as serious.

Adverse events will be recorded and reported as detailed in Section 11.

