4.9 Data listings

Consented patients

Data will be listed for those patients who, after having consented to participate, underwent baseline examinations required for inclusion into the study but who, because a criterion for exclusion was met or for other reasons, were not included in the study. Patient ID and reason(s) for exclusion will be listed.

Withdrawals

Patient ID and all reasons for withdrawal will be listed for patients who have withdrawn from the study.

Medical History (FA)

Medical history will be presented in a line listing, ordered by treatment group and patient ID, of the descriptive text of each event/condition and whether it was classified as past medical history or a presenting complaint.

Adherence with allocated treatment (FA)

Data listings will be provided, ordered by treatment group and patient ID, of the reasons for:

- Temporary stopping of NAC treatment
- Permanent stopping of NAC treatment
- PP100-01 not being given or PP100-01 being stopped early

Protocol deviations and violations (FA)

A listing of protocol deviations and violations will be provided, ordered by treatment group, patient ID and study time point.

Primary outcome (Safety)

Details of adverse events will be listed, ordered by treatment group, patient ID and start date. The listing will include:

- Event category (as recorded on CRF)
- Start date and time
- Date and time resolved
- Seriousness (yes/no)
- SUSAR (yes/no)
- Intensity (mild/moderate/severe)
- Treatment given in response to AE (yes/no)
- Outcome (recovered/improved/unchanged/deterioration/death)
- Relationship to NAC (unrelated/possibly related/probably related/definitely related)
- Relationship to PP100-01 (unrelated/possibly related/probably related/definitely related)
- Action taken with NAC (none/interrupted/stopped entirely)
- Action taken with PP100-01 (none/interrupted/stopped entirely)
- Expectedness with NAC (expected/unexpected/NA)
- Expectedness with PP100-01 (expected/unexpected/NA)

Concomitant Medication (FA)

Three concomitant medication data listings will be provided, one for medications in the 30 days preceding randomisation; the second for medications recorded as “ongoing” at baseline; and a third for those started on or after the date of consent. Each listing will be ordered by treatment group, patient ID and start date, and will contain: Patient ID; Randomisation date; Category; Medication; Start date; Stop date; Ongoing; Dose & Units; Frequency; Route.

5. Derived variables

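### Vomiting and retching episodes must be recorded, but the SAP gives them no row and never uses the count; a descriptive summary should be added

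*SAP*

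**What the plan says.** **Collection.** Protocol 7.1.9: "Episodes and incidence of vomiting and retching will be recorded objectively by nursing staff on the AE log". Protocol 2.3 gives the reason to look closely: "Immediate blood pressure fall, severe diarrhoea and severe vomiting, have previously been identified as important potential risks".

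**Analysis.** SAP 4.4 sets the scale: "The number and percentage of patients experiencing an adverse event (AE) will be summarised by treatment group and overall". The further tables (seriousness, intensity, relationship, action taken, outcome, system organ class) keep that patient-level scale. The primary analysis does the same: "The numbers of participants experiencing AEs and SAEs will be reported by treatment group and overall using the proportion and exact 95% confidence interval", with differences in proportions within each cohort and between each dose and pooled NAC alone. No SAP section mentions vomiting or retching. SAP 4.6 does give anaphylactoid reactions a line of their own.

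**Listing.** SAP 4.9: "Details of adverse events will be listed, ordered by treatment group, patient ID and start date". Its fields include event category, start and resolution times and intensity, but no episode count.

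**Background rate.** Protocol 2.2.2 reports nausea and vomiting on NAC "occurring in 70.4% and 60.4% respectively in a recent cohort of 169 patients treated in Edinburgh". Protocol 3.2 adds: "The 12hr regimen was associated with very significant reductions in anaphylactoid reactions and vomiting compared with the 20.25hr infusion protocol". It gives no figure for the 12-hour regimen.

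**The concern.** Safety and tolerability are the primary objective, and vomiting is both a named risk of the study drug and a common effect of the background treatment. If many patients vomit at least once on NAC alone, extra emetic toxicity from the bolus would appear largely as more episodes in patients who would have vomited anyway. The any-event table cannot show that. The class row cannot either, because vomiting is pooled there with nausea, which was even more frequent in the cited cohort. Intensity is tabulated across all events, so severe vomiting, which is the risk as named, cannot be read from the tables. A dose-related rise could be visible on the ward and absent from every summary table.

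**Working it through.** **1. What is collected against what is reported**

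| Item | Protocol | SAP output |
|---|---|---|
| Any vomiting or retching | Recorded (7.1.9) | No row; inside any AE and one class row |
| Number of episodes | Recorded (7.1.9) | None |
| Severity of vomiting | Graded (10.4.3) | Intensity over all AEs only; listing |
| Anaphylactoid reactions | Outcome (4) | Own line (4.6) |

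**2. Size of the comparisons.** 3 × (6 + 2) = 24, which agrees with the plan. Protocol 12.3 states no power or effect size, so there is no power figure to reproduce. SAP 4.4 compares 6 v 2 within a cohort and 6 v 6 for each dose against pooled NAC alone.

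**3. What a yes/no vomiting row could show.** Exact 95% intervals: 6/6 gives 54.1% to 100% (lower limit 0.025^(1/6)); 3/6 gives 11.8% to 88.2%; 1/2 gives 1.3% to 98.7%. With 6 v 6, Fisher's test reaches p ≤ 0.05 only at 0/6 v 5/6, 0/6 v 6/6 or 1/6 v 6/6, or their mirror images. Suppose 60.4% vomit on NAC alone and every PP100-01 patient vomits. Significance then needs 0 or 1 of 6 on NAC alone:

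0.396^6 + 6 × 0.604 × 0.396^5 = 0.0039 + 0.0353 = 3.9%.

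Barnard's test gives 17.4%. At that background the yes/no scale is close to its ceiling.

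**4. What the count could add.** The documents give no episode distribution. Assume negative binomial counts with dispersion k, and background proportion p0 with at least one episode. Then mean m0 = k[(1 − p0)^(−1/k) − 1], and P(any) = 1 − (k/(k + m))^k. For p0 = 60% and k = 1:

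- m0 = 1/0.4 − 1 = 1.5
- a tripling gives m = 4.5
- P(any) = 1 − 1/5.5 = 81.8%

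So three times as many episodes moves the yes/no proportion only from 60% to about 82%.

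Power was simulated for all PP100-01 patients against all NAC-alone patients (18 v 6), with an exact rank test stratified by cohort (28³ allocations), two-sided 5%, 1,000 trials per setting. In that example, repeat runs gave 28% to 31% on counts and 15% to 17% on yes/no, with a standard error of about √(0.30 × 0.70/1,000) = 1.4 points.

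Part of this gap is test discreteness. With no effect at 60% background, the yes/no test rejects about 2% to 3% of the time and the count test about 3% to 5%. With both tests brought to the same size, the example becomes about 32% v 23%.

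Gain of counts over yes/no for a tripled mean, k from 0.5 to 2:

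| Background | As run | Equal test size |
|---|---|---|
| 60% | 8 to 21 points | roughly 3 to 14 points |
| 45% | 7 to 11 points | not computed |
| 30% | 2 to 5 points | about 0 to 1 point |
| 15% | none (e.g. 2.5% v 2.1% at k = 1) | yes/no slightly ahead |

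**5. The SAP's own 6 v 6 comparison** (tripled mean, k = 1), yes/no by Barnard against a rank test on counts: 7.0% v about 20% at 60.4% background; 11.8% v about 14% at 45%; 12.1% v about 7% at 30%. The ordering reverses at the low end.

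**The case against.** **The background rate may be low.** The 60.4% belongs to the older regimen, whose reactions protocol 2.2.2 links to its high loading dose. The 12-hour regimen reduced vomiting, and a window opening at 2 hours starts after the loading infusion. This stands: the rate in that window is unknown and could be where counts add little or nothing.

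**The 18 v 6 contrast is not in the SAP** and assumes one effect across three doses. This stands; the figures show scale only.

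**Counts are not clearly cleaner.** Protocol 9.6 permits antiemetic rescue. In an open-label trial, rescue after a first episode can lower later counts unevenly between arms. No section defines an episode, and the AE log layout is not shown. This stands, and is why rescue use belongs beside the count.

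**The listing already serves 24 patients.** Only in part. Counts can be rebuilt from it only if each episode is its own row, and it fixes neither a window nor a summary before the data are seen.

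**Stronger readings to avoid.** A reader might infer that the yes/no scale throws away most of the information, or that the count scale can never do worse. Steps 4 and 5 support neither. A reader might also infer a breach of protocol. There is none: protocol 4 lists no vomiting-count outcome, and protocol 12.4 treats the primary outcome as binary.

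**Conclusion.** The point holds as a missed use of data that must be collected anyway, on a named risk and within the primary objective. Vomiting has no row, cannot be separated from nausea in the class table, and its count goes unused. These facts rest on the documents alone.

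The size of the statistical gain rests on assumptions: negative binomial counts, a tripled mean, one effect at all doses, and a background rate that the documents do not give for this regimen. Power is low on either scale, so the benefit is that a reader can see a pattern, not that a test would find one. A reader might want a formal comparison or shift estimate for the counts; small, heavily tied, zero-rich groups do not justify it. SAP 4.4 itself allows a retreat to descriptive summaries. This is a cheap, worthwhile improvement, not a flaw that endangers the trial's conclusions.

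**What to change.** In SAP 4.6, next to anaphylactoid reactions, add a descriptive vomiting/retching summary by treatment group:

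- patients with any episode, as a proportion with exact 95% interval, as in 4.4;
- episodes per patient: median, range and individual values;
- patients with moderate or severe vomiting;
- rescue antiemetic use alongside.

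Split each item into before the PP100-01 bolus and from the bolus to 20 hours, taking 2 hours as the dividing time in NAC-alone patients. This separates vomiting that the study drug could not have caused. Because protocol 10.3 records events only from consent, open the first period at consent or NAC start, whichever is later. State what counts as one episode, and add the episode count to the AE listing in SAP 4.9. Specify no test or shift estimate.

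**Cost.** One table, one listing field and a few lines of SAP text. Episodes must be entered singly or as a count. Later counts must be read with rescue use in view. Sample size and the primary analysis do not change.

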5 STUDY DESIGN

The study will be an open label explorative, randomised, dose rising design, NAC controlled study in patients treated for paracetamol/acetaminophen overdose using the 12hr NAC regime.

Entry into the study will depend on the patient's blood results confirming need for NAC.

Patients that have signed the informed consent will be treated with NAC followed by rising doses of the PP100-01. Each PP100-01 treatment dosing cohort will have 8 patients, 6 randomised to PP100-01 and 2 randomised to NAC alone.

- Group A: PP100-01 (2 µmol/kg calmangafodipir) after the "loading" dose of NAC
- Group B: PP100-01 (5 µmol/kg calmangafodipir) after the "loading" dose of NAC
- Group C: PP100-01 (10 µmol/kg calmangafodipir) after the "loading" dose of NAC

PP100-01 treatment is administered intravenously during 5 minutes.

The standard NAC regime will be continued with the second dose: 200 mg/kg NAC in 1000 ml i.v. over 10hrs.

The patients will continue NAC treatment according to standardised guidelines throughout the study until the patient is considered normalized and can leave the hospital.

The study will primarily evaluate safety and tolerability for treatment with PP100-01 in combination with NAC compared to the 12hr NAC treatment regime.

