7 PATIENT ASSESSMENTS AND DATA COLLECTION

7.1 Description of Assessments

7.1.1 Blood Samples

NAC will be given to all patients arriving to the hospital according to the standard guidelines when paracetamol/acetaminophen overdose is suspected. All patients that arrive to the hospital before 24hrs after POD will be asked if they will participate in the study.

As part of routine clinical care all patients presenting to hospital following a paracetamol overdose will have the following blood tests on arrival to hospital or 4hrs after overdose (whichever is the longer time).

- S-APAP level in serum
- Urea, sodium, potassium and creatinine
- Liver function tests (LFTs) ALT, Bilirubin and ALP
- Clotting screen: INR and Prothrombin time (PT)
- Haemoglobin, White Blood Cells(WBC), Mean Cell Volume (MCV)

Immediately prior to administering PP100-01 a study specific blood sample will be collected (10mL split over serum and plasma) which will measure:

- ALT, bilirubin and alkaline phosphatase (ALP)
- Prothrombin time and INR
- Serum creatinine
- Biomarkers: CK18 and microRNA MiR122, GLDH, mitochondrial DNA and others
- PP100-01 levels

These measurements are part of the sub-study examining novel biomarkers.

As part of routine clinical care there will be blood sampling at 10 hrs and 20 hrs after starting NAC. The following are routinely measured:

- S-APAP level in serum
- Urea, sodium, potassium and creatinine
- Liver function tests (LFTs) ALT, Bilirubin and ALP
- Clotting screen: INR and Prothrombin time (PT)
- Haemoglobin, White Blood Cells(WBC), Mean Cell Volume (MCV)

At these 10hr and 20hr venepuncture episodes study specific blood samples will also be collected (at each time 10mL split over serum and plasma) which will measure:

- Biomarkers: CK18 and microRNA MiR122, GLDH, mitochondrial DNA and others
- PP100-01 levels

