7.1.7 Treatment Phase

Treatment will start with the first NAC bag of 100 mg/kg in 200 ml ("loading dose") at time point '0'. Immediately prior to PP100-01 a study specific blood sample will be collected (time 2hr).

PP100-01 treatment is administered intravenously as a bolus infusion over 5 minutes at the dose specified by the dosing cohort:

- Group A: PP100-01 (2 µmol/kg calmangafodipir) after the "loading" dose of NAC
- Group B: PP100-01 (5 µmol/kg calmangafodipir) after the "loading" dose of NAC
- Group C: PP100-01 (10 µmol/kg calmangafodipir) after the "loading" dose of NAC

All necessary precautions will be taken during administration of the study drug. The patient will be monitored with vital signs (Section 7.1.3). Observation and medical treatment for anaphylactic shock will, as a standard be requisite.

The 12hr NAC regime will be continued with the second dose: 200 mg/kg NAC in 1000 ml i.v. over 10 hr. As per routine clinical practice, there will be one blood sample taken 2 hrs before the end of the second NAC bag (the 10hr time-point) and a second blood sample taken 10h later (the 20hr time-point).

The following procedures should be performed during the treatment phase at time-points: baseline, 2hr, 10hr and 20hr (see study schedule, section 7.2 (Table 1)):

• ALT, bilirubin and alkaline phosphatase (ALP)

- Prothrombin time and INR
- Serum creatinine
- Biomarkers: CK18 and microRNA MiR122, GLDH, mitochondrial DNA and others
- PP100-01 level will be assessed at 2hr, 10hr and 20hr

Any rescue medication given will be recorded in the Case Report Form by routine clinical staff.

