10.3 Detecting AEs and SAEs

All AEs and SAEs must be recorded from the time a participant consents to join the study until hospital discharge.

The Investigator should ask about the occurrence of AEs/SAEs during the infusion and until hospital discharge. Open-ended and non-leading verbal questioning of the participant should be used to enquire about AE/SAE occurrence. If there is any doubt as to whether a clinical observation is an AE, the event should be recorded.

Patient electronic records will be reviewed at 7 days, 30 and 90 days after discharge for AEs and SAEs.

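### SAP 4.4 plans no adverse-event comparison that starts at the PP100-01 dose, so recorded AEs from the NAC-only loading phase can mask part of a PP100-01 excess

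*SAP*

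**What the plan says.** SAP 4.4 states its main comparison this way: "The numbers of participants experiencing AEs and SAEs will be reported by treatment group and overall using the proportion and exact 95% confidence interval". Differences in proportions with exact 95% intervals follow, within each cohort (6 v 2) and for each dose against the pooled NAC-alone patients (6 v 6). No onset limit applies. Two of the further tabulations are limited by onset, one for AEs ("AEs starting after the commencement of NAC treatment and within 7 days of consent") and its counterpart for SAEs. Both open at NAC start.

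Protocol 10.3 fixes when counting begins: "All AEs and SAEs must be recorded from the time a participant consents to join the study until hospital discharge". Protocol 7.1.7 puts the PP100-01 bolus after the 2 h NAC loading infusion ("Immediately prior to PP100-01 a study specific blood sample will be collected (time 2hr").

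How much of the loading phase falls after consent is not settled. Protocol 7.1.1 says "NAC will be given to all patients arriving to the hospital according to the standard guidelines when paracetamol/acetaminophen overdose is suspected", which allows NAC before consent. Protocol 5 gives the other order: "Patients that have signed the informed consent will be treated with NAC followed by rising doses of the PP100-01". The schedule in Protocol 7.2 also places consent and randomisation at screening, ahead of the NAC time-0 column.

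**The concern.** The primary objective is the tolerability of PP100-01 as an add-on to NAC. Up to 2 h of recorded AE time precedes the drug, is the same in both arms, and cannot reflect it. Someone who vomits at 1 h is already counted, so a further AE at 3 h leaves the any-AE proportion unchanged.

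The other AE outputs fill the gap only in part:

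- The system organ class table separates a later event from an earlier one only when they fall in different classes.
- The intensity table separates them only when the later event is graded worse.
- The PP100-01 relatedness table rests on open-label judgement and has no true counterpart in NAC-alone patients.
- The listing in SAP 4.9 shows start times but gives no planned between-arm estimate.
- The anaphylactoid summary in SAP 4.6 follows SAP 4.4 and has no window from the bolus.

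At stake is how clearly the main tolerability table shows what PP100-01 adds.

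**Working it through.** **Plan's own figure.** 3 cohorts × (6 + 2) = 24 patients: 18 on PP100-01 plus NAC and 6 on NAC alone. Protocol 12.3 gives no AE rate, effect size or power, so there is nothing further to reproduce.

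**Set-up.** Let p be the risk of a recorded AE between consent and 2 h, equal in the two arms by randomisation. Let d0 be the PP100-01 excess in post-2 h AE risk among patients with no earlier AE, and d1 the excess among patients with one.

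- Difference in a table that starts at the bolus: (1 − p)·d0 + p·d1
- Difference in the any-AE table from consent: (1 − p)·d0, because everyone with an early AE already counts
- Loss: p·d1

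**Inputs.** The documents give none of p, d0 or d1. I take p from 0 to 40%: near 0 if consent comes late, and held down because Protocol 3.2 credits the 12 h regimen with "very significant reductions in anaphylactoid reactions and vomiting compared with the 20.25hr infusion protocol". For illustration I assume post-2 h AE risks of 20% on NAC alone and 60% with PP100-01.

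**Case 1: the excess does not depend on earlier AEs (d0 = d1 = 40 points).** Any-AE proportion = 1 − (1 − p)(1 − r), where r is the post-2 h risk.

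| p | NAC alone | PP100-01 + NAC | Difference (points) | Expected extra patients in 6 |
|---|---|---|---|---|
| 0 | 20% | 60% | 40 | 2.40 |
| 10% | 28% | 64% | 36 | 2.16 |
| 20% | 36% | 68% | 32 | 1.92 |
| 40% | 52% | 76% | 24 | 1.44 |

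At p = 20% the loss is 0.20 × 40 = 8 points, or 0.48 of a patient in six. With 20% v 50% instead, 30 points become 27, 24 and 18 at p = 10%, 20% and 40%.

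**Case 2: no excess in patients with an early AE (d1 = 0, d0 = 40).** At p = 20% both tables show 0.80 × 40 = 32 points. Nothing is lost.

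**Case 3: excess only in patients with an early AE (d1 = 40, d0 = 0).** At p = 20% the post-bolus table shows 0.20 × 40 = 8 points and the any-AE table shows 0.

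**SAEs.** With an assumed early SAE risk of 2% and a 10-point excess, the loss is 0.02 × 10 = 0.2 points, leaving 9.8.

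**What the sample can show.** The SAP plans no test, so this is only a gauge of sensitivity. Under Case 1, the chance that a two-sided Fisher exact test gives p ≤ 0.05 in 6 v 6 is 8.0% from the bolus and 4.9% from consent with early risk 20%. In 6 v 2 it is 3.0% and 4.1%: only a complete split (6/6 v 0/2 or the reverse, 1/28 = 0.036) reaches the threshold, so the new window brings no gain there.

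**The case against.** The strongest reply is that comparisons around the bolus already exist. Protocol 7.1.3 takes baseline vital signs 1 to 2 h after NAC start and repeats them at 2.5 h. SAP 4.6 analyses them by the SAP 4.5 methods, which include change from baseline, between-arm differences and 95% intervals. ECG at 2.5 h is cross-tabulated against its pre-dose baseline. Protocol 2.3 states the drug's known concerns: "Immediate blood pressure fall, severe diarrhoea and severe vomiting, have previously been identified as important potential risks". The first is therefore covered. For vomiting, the concern is the severe form, and severe vomiting after milder loading-phase vomiting moves the patient into the severe row of the SAP 4.4 intensity table. This stands, and it narrows the gap to non-severe AEs and to later events of the same grade and class.

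The size is also assumed. Early risk may be near 0, the loss depends on an excess in patients with an early AE, and Protocol 2.3 reports no meaningful AE differences from placebo in the earlier calmangafodipir study. With 24 patients a reader can pick out post-bolus events from the timed listing, and SAP 4.4 allows a fall-back to descriptive summaries. This also stands as a limit on weight. It does not supply a pre-specified count, and if the intervals are dropped the counts become the result.

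A post-bolus window does not isolate PP100-01 either. NAC reactions can follow soon after loading, and another 200 mg/kg of NAC runs over the next 10 h. That is correct, and is one reason to keep the new table supplementary.

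**Conclusion.** The gap is real and modest. SAP 4.4 has no between-arm AE comparison that opens at the PP100-01 bolus, and any AE recorded in the loading phase can hide a later one in the any-AE proportion. The loss is p·d1. On the assumed rates in Case 1 it is 4 to 16 points of a 40-point excess for p of 10% to 40%. It is zero if p or d1 is zero. SAEs are barely touched.

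Four stronger readings that a reader might infer are not supported:

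- **That the primary comparison is invalid.** With no PP100-01 effect the expected difference is still zero; the issue is dilution of a real excess.
- **That the 70.4% nausea and 60.4% vomiting rates in Protocol 2.2.2 can serve as p.** They are not specific to the 12 h regimen or to the first 2 h, and Protocol 2.2.2 and 3.2 say the newer regimen was developed to, and did, lower vomiting and anaphylactoid reactions.
- **That the whole loading phase is counted.** The documents disagree on whether consent precedes NAC.
- **That a trial decision is affected.** The pause rules in Protocol 10.10 and the sample size in 12.3 do not use the any-AE proportion.

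**What to change.** In SAP 4.4, add a pre-specified supplementary analysis: the same proportions, differences and exact 95% intervals, within cohort and against pooled NAC alone, for AEs and SAEs starting or worsening at or after the PP100-01 bolus. In NAC-alone patients set time zero at NAC start plus 2 h, or at the recorded end of the loading infusion. State which applies, since SAP 4.3 does not list that end time. Keep the from-consent analysis as primary.

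Report separately patients who leave before 2 h and those whose loading infusion is interrupted (Protocol 9.3), because the interruption moves the anchor. Say how worsening is identified: the SAP 4.9 listing carries one start time and one intensity per event, so a change in grade counts only if it is entered as a new event.

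The cost is one paragraph and one extra set of tables. AE start times are already listed, and the SAP 4.3 timing summaries already need the NAC and PP100-01 start times. The drawbacks are a window that opens after randomisation and, at 6 v 2 or 6 v 6, a gain that is descriptive only.
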